3.5.1 Incidence of medically attended LRTI due to RT-PCR-confirmed RSV

The determination of medically attended RSV LRTI will be based on objective clinical LRTI criteria (described in the Protocol Section 4.3.1.1 and SAP Appendix 1) and RSV test results obtained from analyzing the respiratory secretions using a validated RSV RT-PCR assay for the detection of RSV A or RSV B performed in a central laboratory. These LRTI events may occur in the inpatient or outpatient visit setting.

Based on a blinded review of data, it is determined that a medically attended LRTI will be counted as a medically attended RSV LRTI if there is a respiratory sample tested RSV positive and collected within [-7, 14] days relative to the initial date seen by the healthcare provider (eg, admission/deterioration date associated with the event, urgent care visit, outpatient emergency department [ED] visit, or outpatient clinic visit). In addition, deaths that can be demonstrated as caused by RSV (by autopsy or clinical history and virologic evidence) will also be considered as primary medically attended RSV LRTI events.

3.5.1.1 Analysis of incidence of medically attended LRTI due to RT-PCR-confirmed RSV in Season 1

The incidence of medically attended RSV LRTI (inpatient and outpatient) through 150 days post 1st dose (ie, during a typical 5-month RSV season) in Season 1 is the primary efficacy endpoint and will be summarized by treatment group as well as for all subjects using ITT

population. The 95% Clopper-Pearson (exact) confidence interval of the incidence rate for each treatment group will be produced using the SAS Procedure PROC FREQ with the EXACT statement. For subjects with multiple medically attended RSV LRTI events, only the first occurrence will be used in the summary. Summary of the incidence of medically attended RSV LRTI will also be repeated for CHD subjects and CLD subjects separately.

In addition, the incidence of medically attended RSV LRTI will be further tabulated by Inpatient (primary hospitalization, nosocomial hospitalization) and Outpatient, for the latter category, further presentation will be made by different medical settings: outpatient clinic, urgent care clinic, and ED visits for subjects who did not have a hospitalization due to RSV.

The incidence of medically attended RSV LRTI will also be summarized by the following subgroups:

- Hemisphere
- Age at randomization stratum (age \leq 3.0 months, age > 3.0 to \leq 6.0 months, age > 6.0 months)
- Gender
- Race (Caucasian, non-Caucasian)
- Weight at birth (weight ≤ 2.5 kg, weight ≥ 2.5 kg)
- Weight on Day 1 (weight $\leq 5 \text{ kg}$, weight $\geq 5 \text{ kg}$)
- GA (< 29 weeks, ≥ 29 weeks to < 32 weeks, ≥ 32 weeks to < 35 weeks, ≥ 35 weeks)
- Sibling also participating in the study (yes/no)

In addition, the incidence of medically attended RSV LRTI that occurred through 360 days post 1st dose will be summarized by treatment group.

Age at onset of the first medically attended RSV LRTI through 150 days post 1st dose will be tabulated by age group used for randomization stratification by treatment group. In addition, time-to-first medically attended RSV LRTI will be plotted at subject's level along the axis of age at birth.

The incidence of medically attended RSV LRTI by subtype (RSV A, RSV B) through 150 days post 1st dose, through 360 days post 1st dose will be summarized by treatment group.

To capture and summarize multiple medically attended RSV LRTIs through 150 days post 1st dose, the total number of new onset medically attended RSV LRTIs will be calculated for each subject. A new onset medically attended RSV LRTI is defined as an adverse event (AE) meeting the protocol specified criteria for a medically attended RSV LRTI and occurring at least 14 days after the resolution date of the previous AE for a medically attended RSV LRTI. A similar definition is applied with a 30-day interval between the resolution of the previous

event and onset of a new event (see Table 2 for details). A listing will be generated to provide the following information: age at randomization, hemisphere, total number of events (at least 14 days apart), total number of events (at least 30 days apart), days to event, adverse event (AE) verbatim term, date of AE onset/stop, days from previous event, visit setting, and RSV subtype.

AEs associated with medically attended RSV LRTI will be summarized overall, as well as categorized by MedDRA system organ class (SOC) and preferred term (PT). Summaries will be presented through 150 days post 1st dose, and through 360 days post 1st dose.

Above summaries will be repeated for each cohort (pre-term and CHD/CLD).

3.5.1.2 Analysis of incidence of medically attended LRTI due to RT-PCR-confirmed RSV in Season 2

The efficacy summary in Season 2 (ie, Day 1, Season 2 through Day 361, Season 2) will focus on the CHD/CLD subjects who have been randomized to palivizumab group in Season 1 and enrolled (re-randomized) in Season 2 to either palivizumab or MEDI8897 groups (ie, palivizumab/palivizumab and palivizumab/MEDI8897 groups), to facilitate understanding of the effects of MEDI8897 and palivizumab following an initial treatment by palivizumab in the 1st RSV season. Efficacy data of CHD/CLD subject who have been randomized to MEDI8897 group in both Season 1 and Season 2 (ie, MEDI8897/MEDI8897 group) will also be summarized.

There is no intention to directly compare efficacy of MEDI8897/MEDI8897 group with palivizumab/palivizumab or palivizumab/MEDI8897, since direct comparison between MEDI8897/MEDI8897 and the other 2 arms could potentially be biased if dropouts of Season 1 are associated with efficacy.

All the analyses described above in Section 3.5.1.1 for Season 1 will be repeated for Season 2, with the exception that the weight on Day 1 subgroup summary will be based on Season 2 and the corresponding categories will be: weight < 10 kg, weight $\ge 10 \text{ kg}$.

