3 STATISTICAL METHODS

3.1 General Considerations

There are 3 planned analyses for this study: the primary analysis, the Season 2 analysis and the final analysis. The primary analysis will be conducted after all randomized subjects have completed follow-up through the first 5-month RSV season (ie, Season 1 Day 151 visit) and include all available Season 1 safety, efficacy, PK, and ADA data at the time of the data cutoff. The Season 2 analysis will be conducted after all CLD/CHD subjects have completed follow-up through the second 5-month RSV season (ie, Season 2 Day 151 visit) and include all available Season 1 data and Season 2 safety, efficacy, PK, and ADA data at the time of the data cutoff. The final analysis will be conducted when all subjects have completed the last visit of the study and include all data collected in the study.

At the time of the primary analysis, the Season 1 data will be unblinded to Sponsor/designated clinical research organization associated with the analysis, write-up and submission. To ensure the blinding of Season 2 treatment assignment for CHD/CLD subjects who were randomized to palivizumab arm in Season 1, any data with potential unblinding risk will be split by Season 1 and Season 2 by the corresponding third party data vendors and when the primary database lock (DBL) occurs, only unblinding data from Season 1 will be transferred to the Sponsor for analysis.

The site personnel, participants, and the study team members who participate in the advice or decisions involving study subjects and/or day-to-day interactions with the site, will remain blinded until the end of the study to ensure the trial integrity is maintained. Details of the unblinding process will be documented in a separated file of unblinding plan.

For the visit-based summaries for ADA, RSV neutralizing antibody, RSV serology, and clinical laboratory data, the summaries will be based on the scheduled days with adjusted analysis-defined visit windows. The adjusted analysis-defined windows will be based on the collection schedule listed in the protocol and summaries will be windowed to the closest scheduled visit for those data. Visit windows have been constructed so that every observation collected can be allocated to a particular visit. However, all data will be included in the listings. If multiple readings are recorded within a single analysis-defined visit window, the following rules will apply:

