3.5 Efficacy Analyses

The analyses of the efficacy endpoints, including the incidence of protocol-defined medically attended RSV LRTI (also described as the medically attended RSV LRTI) through 150 days post 1st dose, as well as the incidence of protocol-defined RSV hospitalization (also described as the RSV LRTI hospitalization) through 150 days post 1st dose, will be performed on the respective ITT population for Season 1 and 2. The incidence will be calculated as the proportion of subjects who meet the endpoint during the reporting period. Only summaries will be provided for the efficacy analyses unless specified otherwise. The summaries will be based on observed events.

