3.6.5 RSV resistance monitoring

Nasal samples collected from subjects with RT-PCR confirmed RSV will be subtyped, genotyped, and evaluated by genotypic and phenotypic resistance analyses. Genotypic analyses will report amino acid changes in the mature RSV F protein sequence compared to contemporary reference strains. Phenotypic analyses will report changes in susceptibility of engineered recombinant RSV variants to MEDI8897 and palivizumab neutralization compared to laboratory-derived reference viruses. A detailed description of subjects/samples to be analyzed, sample collection and testing workflow, performance characteristics of assays and methodologies, analysis plans, and reporting plans have been included in a separate clinical virology analysis plan. The details of genotypic and phenotypic analyses and presentation of these data will be included in a separate virology study report.

3.6.6 Incidence of medically attended LRTI from Day 152 to Day 361 for Season 1 and Season 2

For each season, the summaries will be provided using subjects from the respective ITT population who remained in the study at the Day 151 visit. For subjects with multiple medically attended RSV LRTI events after Day 151, only the first occurrence will be used in the summary. More specifically:

• Season 1: The incidence of medically attended RSV LRTI that occurred > 150 days (from Day 152 to Day 361) post 1st dose will be based on RSV test results (performed centrally via RT-PCR) and objective clinical LRTI criteria and will be summarized by treatment group. This endpoint will be further summarized by RSV subtype (RSV A, RSV B) and by treatment group. In addition, AEs associated with this endpoint will be summarized overall, as well as categorized by MedDRA SOC and PT. These summaries will also be provided for each cohort (pre-term, CHD/CLD).

• Season 2: Similar summaries described above for Season 1 will be provided for Season 2 and will focus on the CHD/CLD subjects in the following groups: palivizumab/palivizumab, palivizumab/MEDI8897, and MEDI8897/MEDI8897. who have been randomized to palivizumab group in Season 1 and enrolled (re-randomized) in Season 2 in either palivizumab or MEDI8897 groups. Summaries for CHD/CLD subjects who have been randomized to MEDI8897 group in both Season 1 and Season 2 will also be provided.

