3.7.1 Adverse Events and Serious Adverse Events

Adverse events and serious adverse events will be coded by MedDRA version 22 or higher and the type, incidence, severity and relationship to study investigational product will be summarized by treatment group. Specific AEs will be counted once for each subject for calculating percentages. In addition, the total number of AEs will also be provided. In addition, if the same AE occurs multiple times within a particular subject, the highest severity and level of relationship observed will be reported. All treatment-emergent AEs (TEAEs) and treatment-emergent SAEs (TESAEs) occurring through Day 361 will be summarized overall, as well as categorized by MedDRA SOC and PT. In addition, the TEAEs occurring at 1% or higher in either treatment group will be reported by PT.

Nontreatment-emergent AEs/serious adverse events (SAEs), defined as AEs/SAEs that occur prior to the administration of investigational product, or after Day 361, Season 1 for preterm cohort, or after Day 361, Season 1 and prior to Day 1, Season 2 for CHD/CLD cohort, or after Day 361, Season 2 for CHD/CLD cohort, or pre-planned surgeries that are coded with PT "Cardiac Operation" and occur during the study for CHD subjects will be presented in the listings.

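### At the primary and Season 2 analyses, crude incidences over windows that end at Day 361 include infants not yet followed that long, so absolute rates are understated

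*SAP*

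**What the plan says.** SAP 3.1 (and Protocol 4.8.1) sets three analyses. The primary analysis waits for every randomized infant to finish Season 1 Day 151 and will "include all available Season 1 safety, efficacy, PK, and ADA data at the time of the data cutoff". The Season 2 analysis has the matching trigger at Season 2 Day 151 in the CLD/CHD cohort. Only the last one waits for complete follow-up: "The final analysis will be conducted when all subjects have completed the last visit of the study".

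The incidence measure is fixed in SAP 3.5: "The incidence will be calculated as the proportion of subjects who meet the endpoint during the reporting period". It counts observed events. No Kaplan-Meier, person-time or exposure-adjusted rate is planned.

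The affected summaries and their denominators are:

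- RSV LRTI through 360 days: SAP 3.5.1.1 says "the incidence of medically attended RSV LRTI that occurred through 360 days post 1st dose will be summarized by treatment group". SAP 3.5.3 puts its own through-360-day summaries on the full ITT population.
- RSV LRTI from Day 152 to 361: in SAP 3.6.6, "the summaries will be provided using subjects from the respective ITT population who remained in the study at the Day 151 visit".
- Adverse events: in SAP 3.7.1, "All treatment-emergent AEs (TEAEs) and treatment-emergent SAEs (TESAEs) occurring through Day 361 will be summarized overall". SAP 3.7 uses the as-treated population. Its Table 3 runs the Season 1 window to Day 361 or to the day before Season 2 Dose 1 if that is earlier, and the Season 2 window to Season 2 Day 361. AESIs and NOCDs (SAP 3.7.2 and 3.7.4) have no shorter window of their own.

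**The concern.** An infant dosed late in accrual may have a Day 361 that lies after the cutoff. In a crude proportion that infant is in the denominator for the whole window, and the days not yet lived through count as days without an event. Requiring an infant to be in the study at Day 151 removes earlier dropouts. It does not remove infants whose follow-up the cutoff ends between Day 151 and Day 361.

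Safety is the primary objective, and Protocol 4.8.1 links the primary-analysis data to the write-up and regulatory submission. Yet the SAP has no overall TEAE, TESAE, AESI or NOCD table that stops at Day 151, the last day the trigger guarantees for everyone still in the study. The late RSV summary is meant to show whether MEDI8897 has an effect after Day 151 (Protocol 3.2.3), which is exactly the period that is cut short.

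**Working it through.** **The plan's own figures.** SAP 2.4 gives 600 infants, a true AE rate of 0.5% and a 95% chance of at least one event.

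- 1 − 0.995^600 = 0.9506, which agrees.
- With zero events, the one-sided 95% upper bound is 1 − 0.05^(1/600) = 0.498%, below 0.5% as stated.
- 0.06 × 600 = 36 and 0.06 × 300 = 18 RSV LRTI events, as stated.

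The documents give no expected incidence through Day 361 and no accrual pattern, so the rest is illustration.

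**Inputs.**

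- RSV LRTI of 6% through Day 150 (SAP 2.4).
- A late window of 210 days.
- Assumed: a share f of infants has reached Day 361 at cutoff. The rest are cut off either all at Day 151 (worst case) or uniformly over Days 151 to 361.
- Assumed: a late daily hazard equal to the early one, or a quarter of it.
- No dropout.

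**True values.** The early daily hazard is h = −ln(0.94)/150.

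- Late hazard 1×: Day 152–361 incidence = 1 − exp(−210h) = 8.30%. Through Day 360 = 0.06 + 0.94 × 0.0830 = 13.80%.
- Late hazard 0.25×: Day 152–361 incidence = 1 − exp(−52.5h) = 2.14%. Through Day 360 = 0.06 + 0.94 × 0.0214 = 8.01%.

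**Crude proportions as planned.** The Day 152–361 value is f × (true late value) + (1 − f) × r. Here r = 0 if the rest are cut at Day 151. With uniform cutoffs r is the average of 1 − exp(−h′t) over t from 0 to 210, where h′ is the late hazard; at 1× this is 4.21%. The multiplier is therefore f in the first case and close to (1 + f)/2 in the second. The through-Day-360 value is 0.06 + 0.94 × (crude late value).

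| f | Late hazard | Day 152–361 | Multiplier | Through Day 360 | Multiplier |
|---|---|---|---|---|---|
| 0.90 | 1× | 7.47–7.89% | 0.90–0.95 | 13.02–13.42% | 0.94–0.97 |
| 0.90 | 0.25× | 1.93–2.04% | 0.90–0.95 | 7.81–7.91% | 0.97–0.99 |
| 0.75 | 1× | 6.22–7.28% | 0.75–0.88 | 11.85–12.84% | 0.86–0.93 |
| 0.75 | 0.25× | 1.61–1.88% | 0.75–0.88 | 7.51–7.76% | 0.94–0.97 |
| 0.50 | 1× | 4.15–6.25% | 0.50–0.75 | 9.90–11.88% | 0.72–0.86 |
| 0.50 | 0.25× | 1.07–1.61% | 0.50–0.75 | 7.01–7.51% | 0.87–0.94 |

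The longer window suffers less because its first 150 days are complete.

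**A rare adverse event.** Suppose the 0.5% rate refers to 360 days at constant hazard (the SAP does not say). At f = 0.50 the crude rate is 0.35–0.43%, and the chance of at least one event in 600 falls from 95% to 88–92%.

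**Between arms.** Randomization is concurrent, so both Season 1 arms should share the same f. With f = 0.50 and the rest cut at Day 151, true late rates of 4% and 6% become 2% and 3%. The ratio stays at 0.67.

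**The case against.** The strongest reply is that the SAP never says the Day 361 tables run early. SAP 3.1 lists the data in each analysis, not the tables, and SAP 1 leaves table specifications to a separate programming plan. That is correct, so early production is an inference. Two passages support it. SAP 3.7 says that every planned safety analysis will be presented for each season. SAP 3.6.1, which reports through 360 days, has a hospital-stay rule that names the data cutoff date of the primary analysis.

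A second reply points to safeguards. SAP 3.4.1 tabulates disposition at Day 151 and Day 361, and SAP 3.7.5 summarizes events within 1, 3, 7 and 14 days of dosing. The first shows how mature the data are but does not correct a percentage. The second gives short windows that should be complete, but no overall safety table. The final analysis does supply complete figures, so nothing is permanently understated.

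A reader might go further in four ways that the documents do not support:

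- That many infants will have been followed only to about Day 151. Day 151 is the minimum, set by the last infant, and no accrual dates are given.
- That the Day 152 to 361 incidence is divided by all infants. SAP 3.6.6 restricts it to those still in the study at Day 151.
- That the results could not be set beside the Phase 2b safety figures. Protocol 1.4.1 takes those from a primary analysis with the same Day 151 trigger, and neither study's follow-up distribution is given.
- That Season 1 figures are also short at the Season 2 analysis. Season 1 Day 361 may coincide with Season 2 Day 1 (Protocol Table 5, footnote), so Season 1 follow-up is essentially over by then.

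Constant hazard is also a simplification, because RSV is seasonal. That is why two late hazards are shown.

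**Conclusion.** The point holds for absolute incidence at two analyses: Season 1 figures at the primary analysis, and Season 2 and Season 1 + Season 2 figures at the Season 2 analysis. It covers TEAEs, TESAEs, AESIs and NOCDs through Day 361, RSV LRTI through 360 days, and RSV LRTI from Day 152 to 361. The direction is certain if any infant's follow-up is cut off before Day 361 and late events can occur. The size is not known: the multipliers above rest on assumed values of f, assumed cutoff patterns and assumed late hazards. If nearly all infants have reached Day 361, the effect is small.

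The Season 1 between-arm comparison, the 150-day efficacy endpoint and the final analysis are not biased by the cutoff. The change is worth making because safety is the primary objective and the remedy needs no new data.

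**What to change.** In SAP 3.1, state which Day 361 tables are produced at each analysis. At the primary and Season 2 analyses:

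- Add overall TEAE, TESAE, AESI and NOCD tables through Day 151 of the season, as the complete-follow-up safety summary.
- Give RSV LRTI from Day 152 to 361 and through 360 days as Kaplan-Meier estimates censored at the cutoff, with the number followed to Day 361 in each arm. Alternatively, reserve these summaries for the final analysis.

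Keep the crude proportions for the final analysis, where follow-up is complete.

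The cost is SAP wording and one extra set of tables at two analyses. No visit, sample or data item is added.

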3.5.1.3 Sensitivity Analyses of incidence of medically attended LRTI due to RT-PCR-confirmed RSV

Sensitivity analyses will be carried out for incidence of medically attended RSV LRTI based on the following population for each season:

• ITT subjects excluding who received any dose of wrong treatment (ie, subjects who were randomized to palivizumab group but received MEDI8897 or placebo, and subjects who were randomized to MEDI8897 group but received palivizumab during the season), or missed any active dose, or had at least 1 active dose out of 7-day window.

3.5.2 Incidence of RSV hospitalization

The events of "RSV hospitalization" are a subset of "medically attended RSV LRTI," which are determined based on objective clinical LRTI criteria (described in the Protocol Section 4.3.1.1 and SAP Appendix 1) and RSV test results obtained from central laboratory analysis respiratory secretions using a validated RSV RT-PCR assay for the detection of RSV A or RSV B.

3.5.2.1 Analysis of Incidence of RSV hospitalization in Season 1

The incidence of RSV hospitalization through 150 days after dosing in Season 1 (ie, during the 5-month RSV season) will be summarized by treatment group for each cohort as well as for all subjects. For subjects with multiple RSV LRTI hospitalizations, only the first occurrence will be used in the analysis.

For each treatment group, age at onset of the first medically attended RSV LRTI hospitalization will be tabulated by age group used for randomization stratification by treatment group. In addition, time-to-first medically attended RSV LRTI hospitalization will be plotted at subject's level along the axis of age at birth. RSV LRTI hospitalization will also be summarized by RSV subtype (A or B). The incidence of RSV LRTI hospitalization will also be summarized by the following subgroups.

- Hemisphere
- Age at randomization stratum (age \leq 3.0 months, age > 3.0 to \leq 6.0 months, age > 6.0 months)
- Gender
- Race (Caucasian, non-Caucasian)
- Weight at birth (weight ≤ 2.5 kg, weight ≥ 2.5 kg)
- Weight on Day 1 (weight $\leq 5 \text{ kg}$, weight $\geq 5 \text{ kg}$)
- GA (< 29 weeks, ≥ 29 weeks to < 32 weeks, ≥ 32 weeks to < 35 weeks, ≥ 35 weeks)
- Sibling also participating in the study (yes/no)

Above summaries will be repeated for each cohort (preterm and CHD/CLD).

3.5.2.2 Analysis of Incidence of RSV hospitalization in Season 2

The efficacy summary in Season 2 (ie, Day 1, Season 2 through Day 361, Season 2) will focus on the CHD/CLD subjects who have been randomized to palivizumab group in Season 1 and enrolled (re-randomized) in Season 2 in either palivizumab or MEDI8897 groups (ie, palivizumab/palivizumab and palivizumab/MEDI8897 groups), to facilitate understanding the effects of MEDI8897 and palivizumab following an initial treatment by palivizumab in the first RSV season. Efficacy data of CHD/CLD subjects who have been randomized to

MEDI8897 group in both Season 1 and Season 2 (ie, MEDI8897/MEDI8897 group) will also be summarized.

All the analyses described above in Section 3.5.2.1 for season 1 will be repeated for season 2, with the exception that the weight on Day 1 subgroup summary will be based on Season 2 and the corresponding categories will be: weight < 10 kg, weight $\ge 10 \text{ kg}$.

